**Anticipated results, potential pitfalls, alternative approaches, future directions:** We expect that delayed eating + alcohol consumption will be associated with imbalance in Th17/Treg/Neutrophil profiles, mucosal hyperproliferation, increased proliferation rate, and reduced apoptosis. Such observations would support our overall hypothesis that delayed eating in subsets of alcohol users, worsens circadian disruption associated with a pro-carcinogenic inflammatory milieu, which if not addressed for months or years will promote tumorigenesis. It is possible that circadian disruption, in addition to alterations in selected immune markers, or independent from them, enhances alcohol-induced carcinogenesis via other alcohol-related mechanisms, such as oxidative stress. Therefore if the immune pathways are not involved in mediating circadian effects, markers of

additional/alternative pathways (e.g., iNOS and NF- $\kappa$ B for oxidative stress) could be examined in the future. Besides Treg/Th17 and neutrophils, global RNA gene expression can be regressed against outcomes in this study, further refining pathways that are associated with eating pattern, alcohol, or their combination. From the RNAseq coexpression analysis we expect to define major biological processes which are the substrates and downstream correlates of altered circadian rhythms. We expect the altered immune profile to correlate with mucosal proliferative profiles and dysbiosis. We expect these changes to correlate with circadian dysrhythmia, measured in Aim 2. But in the event there is no relation between circadian disruption and mucosal markers, other mechanisms may mediate the effect of delayed eating on alcohol-induced tissue injury. For example, metabolic pathways (e.g., mTOR) are linked to CRC and are entrained by food, and can be investigated by gene expression profiling of the biopsies obtained in this Aim. This Aim will let us generate an integrated map of the immune response to delayed eating, alcohol and circadian dyssynchrony. Results from the microbiome analysis will identify the upstream signals that can signal the upregulation or downregulation of genes and pathways that modulate the inflammatory response. Although it would be ideal to study pre-cancerous lesions/polyp, we cannot subject polyps to RNA analysis as the histology of the entire polyp must be reviewed by a clinical pathologist to exclude any possible cancerous changes. On the other hand, cancer is the end product of accumulating events and will not be appropriate for our purpose of identifying early signatures for alcohol induced carcinogenesis. We will therefore profile biopsies from “normal” appearing mucosa”, but from the tissue of a subject that recently harbored an advanced adenoma and thus their sigmoid mucosa is expected to have a “field defects”. Prior studies have shown that abnormal mucosal signatures in patients with CRC are field defects and are present in the normal appearing colonic mucosa. To maximize the field effect in our subjects with advanced adenoma, we will recruit those with sigmoid lesions in whom the abnormalities are expected to occur in our biopsy field. Biopsy materials contain a small number of immune cells. Thus, we will use Cibersorting of RNA-seq data to identify immune profiles associated with delayed food timing and alcohol. Our data show that RNA-seq data from Cibersorting analysis is feasible to identify impact of circadian disruption on immune cells [Data not shown]. Alternatively, we will perform immunostaining of sigmoid biopsies for our immune candidates which can also be used for validation of the Cibersorting. As in Aim 2, we will do an interim analysis after the first 6 subjects and prolong the intervention duration if 1 week is insufficient to see changes in the mucosal readouts. Prior studies showed that type and time of diet rapidly (<1 week) alter the gut microbiome. Coexpression analysis will identify coexpressed gene sets which gain or lose correlation under alcohol and/or circadian perturbations in humans associated with other traits measured in each subject such as dysbiosis and mucosal proliferation. Subset of these coexpressed gene sets may be enriched in differentially expressed genes from mouse disease models in Aim 1, which will establish key components of those models and identify what aspects of human effects they best represent. Collectively these systems-level results will establish the major biological processes associated with specific components of alcohol and circadian disruption.

**Statistics and Overview of data analysis.** A sample size of 44 achieves 81% power to detect 0.1 mean changes in circadian rhythm profiles measured by melatonin and circadian gene expression and changes in immune gene expression and carcinogenesis markers (proliferation, apoptosis and DNA markers) within a subject with an estimated standard deviation of differences of 0.3 under a significance level (alpha) of 0.05 using a two-sided paired t-test. Power will be increased by using multivariable regression including other covariates that may affect the outcomes including demographics such as gender, BMI, age, race and chronotype. Repeated Measure ANOVA with two factors (alcohol, eating pattern) and their interaction (alcohol\*eating) will be used. To control various types of additional predictors other than alcohol and eating conditions, a Generalized Estimating Equation (GEE) model approach will be used.

**I. Generation of immune profiles in response to alcohol and abnormal food timing:** In Aim 1, RNA-seq, will be done to infer Treg/Th17/neutrophil profiles, associated with worsening polyposis in response to alcohol and abnormal eating patterns (or each alone). The immune signature will be used for profiling the gene expression data from mucosal biopsy tissues obtained in Aim 3a.

**II. Immune profiling from sigmoid tissue:** In Aim 3a, RNA-seq will be done on biopsies followed by immune profiling using CIBERSORT. Immune signatures determined in Aim 1a will be used as a guide to interrogate the profiles obtained from endoscopic sampling in response to alcohol or delayed food timing, or both.

**III. Microbial composition and structure:** 16S rRNA amplicons will be sequenced using an Illumina MiSeq instrument, with an anticipated output of 50,000 sequences per sample. The surveys of microbial genes generated by deep-sequencing will be used for microbial composition profiling using the Bioconductor R package metagenomicSeq and diversity analysis with the Shannon’s index using the

R package Vegan. **IV. Correlation with Study outcomes:** Differential RNA-seq gene and pathway signatures will be regressed against outcomes in this study separately: the mucosal markers (Aim3b), dysbiosis (Aim3c) as well as circadian rhythm profile (Aim2). This will refine the pathways that are associated with each eating pattern, alcohol, or their combination. The microbiota data will be correlated with the RNA-seq data in Aim3a to determine gene correlates of alterations in immune (Th17/Treg/Neutrophils) profiles in response to study variables (alcohol and food timing) with microbiota population complexity and abundance. **IV. Integrated analysis:** Using an integrated systems biology/network analysis approach, we will look for interactions among immune profiles generated by gene expression data (cibersorting) and microbiome signatures against epithelial proliferations markers as well as circadian measurements (Aim2). Bioinformatics workflow uses the R [www.r-project.org] and Bioconductor platform, and the public databases MsigDB InnageDB. This integrative approach will enable us to identify the effect of eating patterns, in individuals who drink alcohol, on CRC-relevant inflammatory profile and CRC markers, and can interrogate the role of microbiota as a possible mediator. Incorporating data from Aim 2 into our model, we study the role of central-intestinal circadian dyssynchrony induced by alcohol and delayed eating as the driver of the anticipated outcomes in Aim 3.

1. Fedirko, V. et al. Alcohol drinking and colorectal cancer risk: an overall and dose-response meta-analysis of published studies. *Ann Oncol* **22**, 1958-72 (2011).
2. Zhu, J.Z. et al. Systematic review with meta-analysis: alcohol consumption and the risk of colorectal adenoma. *Aliment Pharmacol Ther* **40**, 325-37 (2014).
3. Aleksandrova, K. et al. Combined impact of healthy lifestyle factors on colorectal cancer: a large European cohort study. *BMC Med* **12**, 168 (2014).

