**Methods:** Forty-four individuals (22 men and 22 women) with no history of alcohol use disorder [AUD] who have had advanced tubular adenoma in their sigmoid/descending colon within the last year will be recruited for a randomized cross-over experiment, testing alcohol use +/- two eating conditions on central and digestive tract circadian rhythms. To decrease diet variability of subjects, we will use a validated food frequency questionnaire (FFQ) to assess dietary habits over

[figure not shown]

**Fig 5.** Shift of central circadian rhythm, measured by melatonin profile occurs in night shift workers, and not in day workers, after moderate alcohol.

**Fig 6.** Peripheral rhythm assessed by Clock gene expression in PBMCs before (solid line) and after (dotted line) alcohol, in day & night shifters.

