the prior three months, to exclude subjects on special diets (e.g., vegetarian, gluten-free) and recruit individuals who meet criteria for a typical American diet consisting of daily fiber  $\leq$  16 grams and daily saturated fat  $\geq$  11 grams. All subjects will be  $\geq$  21 years old [expected to be over 50 years old because of a history of polyps], and will be recruited after reviewing the endoscopy database of Rush University's Gastroenterology Division. Exclusion/inclusion criteria, definition of AUD and advanced adenoma are described in Human Subjects. Subjects are asked to avoid any alcoholic drinks for one week prior to each study. One week prior to the study, subjects complete the food/sleep questionnaire/(FSQ) (see Human Subjects) to record baseline food/sleep patterns. Sleep patterns will also be recorded by wrist actigraphy (Actiwach 2, Phillips Inc.). Each subject will undergo four conditions (each for one week in duration with a week wash-out in between [Fig 7]. The order of experiments will be randomized [concealed randomization]. A 24h food recall will be completed by participants using ASA24 at baseline and once during each intervention. This will be used to both determine that dietary intake is kept constant throughout the study, but also to verify time of eating on the FSQ in each of the treatment periods. "Right-time eating" is defined as breakfast (no later than 8am), lunch (no later than 1pm) and dinner (no later than 6pm), while "delayed eating" will be applied by delaying each meal by 3h. The choice of 3h is based on prior reports that alteration in the meal time for 3h can affect weight. Subjects will continue their regular energy and macronutrient content. All attempts will be made to keep sleep-wake periods constant between 11pm and 7am  $\pm$  2 hours. The limit of 2 hours was selected because sleep/wake periods over 2 hours would lead to disrupted circadian rhythms. Adherence to the protocol will be monitored via the FSQ. Subjects will enter the Biological Rhythms Research Lab after each week of the intervention period for 24h for assessments of central circadian rhythms (hourly salivary melatonin) and peripheral clock genes of the digestive tract from mucosal cells taken from buccal swaps once every 2h (12 time points). Extracted cells will be analyzed for expression levels of clock genes (*Per2*, *BMAL1*, *Clock*, *Cry1*, *Reverb-alpha*, *ROR-alpha*). While frequent endoscopic sampling of the intestine is not practical in humans, frequent buccal sampling is the most feasible method to assess the intestinal circadian rhythm^86. Further, using buccal sampling is an acceptable method to assess the digestive tract rhythm, as the intestinal cells have common zeitgebers (SCN, food and GI hormones). Nonetheless, we will also collect rectal swab every 12 hours (2 time points; first sample at the time of sigmoidoscopy) to validate that buccal sample represent disruption of digestive tract circadian rhythmicity by delayed eating. Our prelim data show feasibly of RNA analysis of clock genes from rectal swabs (Fig 8). The observed reciprocal RNA expression of the clock positive limb (*Bmal1* and *Clock*) vs. negative limb (*Per2* and *cry1*) members is suggestive of an expected anti-phasic pattern. Rectal swab sampling more than twice is not practical. Although the rhythm of proximal part may phase-advance the distal part of the digestive tracts, rhythm of different segments of GI tracts are still in synchrony to maintain a healthy physiologic homeostasis. Therefore buccal rhythm, though not a direct predictor of colonic rhythm, fits our purpose of assessing alteration of digestive tracts rhythm of subjects in response to our intervention (alcohol or food timing). For alcohol-related experiments, subjects will be given bottles of red wine and asked to drink wine with dinner (0.5 g/kg) for the week prior to the Lab visit. We have shown that this protocol causes disruption of circadian genes in PBMC [Fig 6] and promote systemic inflammation (unpublished data). To increase compliance, each subject is given enough bottles of wine to share with his/her partner at dinner.

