Therefore we use FFQ at inclusion to minimize dietary variability among subjects. Prior reports indicate that individuals maintain a consistent dietary pattern over time and compensate for changes in energy intake over the short-term. Thus, it is expected that the subjects during our study period will maintain a consistent pattern of intake. In addition, the potential effect of the differences in energy and macronutrient intake at various time points throughout the day will be mitigated by the use of the cross over design. Further, we collect dietary composition data during the study period which will be used for post-hoc analysis of the potential modulating effect of type of diet on alcohol-induced effects. We selected a one-week period for each intervention as this time is sufficient to see changes in circadian rhythms in response to alcohol [Fig 6], and food [Fig 2]. However we will re-evaluate this time selection following the first six subjects, and if, in the unlikely event we do not see any clear evidence of dyssynchrony, we will increase the intervention time to 10 days. One-week wash-out should also be sufficient to see the recovery from each intervention. Likewise, after the first six subjects, we will see if the wash-out period is adequate; if not, we will increase wash out times to 10 days. We will recruit 44 patients per our calculated sample size (see below). We plan to recruit 55 subjects, assuming 20% drop out (due to the length of the study). In our cross over study, every case acts as its own control, eliminating the need for large sample sizes that would have been required to account for inter-individual heterogeneity. Human circadian studies have a smaller sample sizes due to multiple time point data obtained for every subject, and the intensive nature of the protocol like ours with four of 24hr phase assessments in the Lab where subjects are kept awake. Indeed, a highly cited circadian study reported their findings with n of 5.

**Aim 3: To determine how disruption of circadian homeostasis by delayed eating promotes alcohol-induced colon carcinogenesis in susceptible subject.**

[figure not shown]

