Each subject will experience four conditions (each for one week in duration with a week +/- 2 days wash-out in between): (1) "right-time eating" / no alcohol, (2) "right-time eating" / with alcohol, (3) "delayed-eating" / no alcohol, (4) "delayed-eating" / with alcohol. The order of experiments will be randomized [concealed randomization]. All subjects will undergo unprepped sigmoidoscopy after each week of intervention. In Aim 2, all subjects will have an option to undergo a 24h circadian assessment in the Biological Rhythms Research Lab after each week of intervention. We will assess (i) central circadian rhythms by collecting hourly salivary samples for melatonin assays and (ii) peripheral rhythm in the intestinal tract by buccal swabs once every 2h (12 time points) as well as by rectal sampling twice (every 12 hr). For Aim 3, sigmoidoscopy without sedation will be used to obtain colonic samples as the safe method compared to colonoscopy, which has some small but finite risks associated with the procedure (e.g. bleeding or perforation) as well as sedation.

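### Neither balanced condition orders nor a period term is stated, which leaves modest, avoidable noise (not bias) that a Williams list and a period factor would largely remove

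*Protocol*

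**What the plan says.** In the Protocol, section C (Approach), Aim 2 Methods, the design is: "Each subject will undergo four conditions (each for one week in duration with a week wash-out in between". On order, the text says only: "The order of experiments will be randomized [concealed randomization". Section 4.1.1 a repeats that rule and gives the wash-out some play: "Each subject will experience four conditions (each for one week in duration with a week +/- 2 days wash-out in between". The readable text mentions no sequence set, Latin or Williams square, block or stratum. Figure 7, cited for the design, is not shown.

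The target is "Forty-four individuals (22 men and 22 women) with no history of alcohol use disorder". The recruitment number is larger: "We plan to recruit 55 subjects, assuming 20% drop out (due to the length of the study".

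Statistics and Overview of data analysis names a repeated-measures ANOVA with alcohol, eating pattern and their interaction. It adds multivariable regression on subject characteristics and a GEE approach for further predictors. Period is not named in any of these. The power statement is "A sample size of 44 achieves 81% power to detect 0.1 mean changes in circadian rhythm profiles", with an "estimated standard deviation of differences of 0.3 under a significance level (alpha) of 0.05 using a two-sided paired t-test".

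**The concern.** Four intervention weeks and three wash-outs span about seven weeks, and the periods are not alike. Only the first is not preceded by an earlier intervention week and its sigmoidoscopy with 20 biopsies. For subjects who accept the 24-hour assessment, later periods also follow a session that the protocol describes as "the intensive nature of the protocol like ours with four of 24hr phase assessments in the Lab where subjects are kept awake". The outcomes are circadian and mucosal markers, so a first-period difference or a drift is plausible. The protocol itself leaves the adequacy of the wash-out to be judged after six subjects, which makes balance over the preceding condition useful.

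If the 24 possible orders are drawn freely for 44 subjects, neither kind of balance is assured. If the model also omits period, the period differences stay in the within-subject error. What is at stake is precision, chiefly for the alcohol-by-eating interaction.

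**Working it through.** **Inputs from the protocol.** 4 conditions in 4 periods; 44 subjects (22 per sex); 55 recruited for 20% drop-out; SD of a within-subject difference 0.3. **Assumed, not in the protocol:** free draws from the 24 orders, a linear drift of δ per period, the same SD of 0.3 for every pair of conditions, and that this 0.3 excludes drift.

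**1. The plan's own figures.** The drop-out figure reproduces: 44/0.8 = 55. The power figure does not: the noncentrality is (0.1/0.3) × √44 = 2.21 on 43 degrees of freedom, and two-sided power is 58.0%, not 81%. That is a separate matter which balanced order cannot repair, but it means there is little precision to spare.

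**2. Balance under free order.** Each condition-by-period count is binomial (44, 1/4): mean 11, SD √(44 × 0.25 × 0.75) = 2.87. In simulation the smallest and largest of the 16 counts average 6.2 and 16.3. A four-sequence Williams square with 11 completers per sequence gives 11 in every cell. It also gives each of the 12 ordered adjacent pairs 132/12 = 11 times (3 transitions × 44 = 132).

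**3. Cost if period is not fitted.** The interaction contrast has coefficients (1, −1, −1, 1), with sum of squares 4. Under a random order, drift adds per-subject variance 4 × (5δ²/3) = 6.667δ², where 5δ² is the sum of squared deviations of the four equally spaced period effects.
- Interaction variance per subject without drift: 4 × 0.3²/2 = 0.18, so SE = √(0.18/44) = 0.064.
- Relative increase: 6.667δ²/0.18 = 37.0δ².

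| δ per period | Drift, period 1 to 4 | Added SD, √(6.667δ²/44) | Added variance |
|---|---|---|---|
| 0.03 | 0.09 | 0.012 | 3% |
| 0.05 | 0.15 | 0.019 | 9% |
| 0.10 | 0.30 | 0.039 | 37% |

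Simulation agrees: an SD of 0.129 times the total drift, which is 0.039 at a total of 0.3. For a difference between two conditions the ratio is the same, 2 × (5δ²/3)/0.09 = 37.0δ². If only period 1 differs, by 0.1, the added variance is 0.1²/0.18, about 6%.

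**4. Cost if period is fitted.** Variance under free order relative to the balanced square, from simulated draws:
- Period fitted: mean efficiency 0.977 for the interaction, a loss of about 2%.
- Period and first-order carry-over fitted: mean efficiency 0.953, about 5%. The 5th percentile is 0.855, and 1/0.855 = 1.17, so about 17% in the worst 5% of draws.

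**5. How well balance survives.** 55/4 = 13.75 and 22/4 = 5.5, so neither the recruitment number nor the sex split divides evenly. Allocating 55 from the square and losing 11 at random keeps exact period balance in only about 3% of simulated trials. Average efficiency with period fitted is still about 99.5%. 56/4 = 14 is exact, and 56 × 0.8 = 44.8 preserves the completer target.

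**The case against.** The strongest reply is that nothing here is an error. The protocol does not say that order is unrestricted, and a Williams list would satisfy its sentence. Sequence lists often sit in a separate randomisation plan, and the design figure is not visible. The GEE could take a period term. Randomised order is valid: drift enters each subject's contrast and hence the estimated SD, so the test keeps its size. Part of the period argument is also soft. The 24-hour session is optional, and Aim 3 speaks of comparing samples before and after each intervention, which would offset some level drift. All of this stands, and it limits the point to a precision improvement.

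A reader might infer more in three ways, and the documents support none of them.
- **That imbalance biases the interaction.** It does not; over randomisations the error averages to zero.
- **That a third of the precision is being lost.** The 37% needs a drift of 0.3 across the trial, equal to the whole planning SD and three times the planned change. No drift is given. Nor can the 5% error bound at that drift (about 0.077 on the four-cell interaction) be set against the planned 0.1, which is a paired mean change.
- **That a Williams square fits exactly, removes all imbalance and costs nothing.** It fits 44 completers, but not 55 recruited or 22 per sex, and drop-out will almost always disturb it. Fixed blocks of four would also make later assignments easier to guess, because subjects cannot be masked to wine or meal times and the investigator examines them before randomisation.

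**Conclusion.** The point holds as a low-cost refinement. As written, the plan neither balances order nor names a period term, so it accepts avoidable noise. The realistic gain from balancing is about 2% of variance with period fitted and about 5% with carry-over as well, with a worse tail of about 17%. The larger figures apply only if period is left out, and they scale with the square of an unknown drift. All figures assume that orders would otherwise be drawn freely. If a separate randomisation plan already uses balanced sequences, only the period term remains to be added. The square and the period factor complement each other: the square secures near-balance at allocation, and the factor deals with what drop-out and the optional 24-hour assessment undo.

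**What to change.** In Aim 2 Methods and in section 4.1.1 a, state that each subject's order is one of the four sequences of a Williams square. Assign it by concealed allocation in blocks of 4 and 8 in random order, so that assignments cannot be predicted. Allocate 56 rather than 55 (14 per sequence), and do not require exact balance within sex.

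In Statistics and Overview of data analysis, add period as a fixed factor to the repeated-measures and GEE models.

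The cost is a different randomisation list, one more subject, and three degrees of freedom. With 44 completers the within-subject error falls from 129 (176 − 44 − 3) to 126.

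### The 81% power claimed for 44 subjects does not follow from the printed inputs, which give 58%

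*Protocol*

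**What the plan says.** The paragraph on statistics and data analysis at the end of Section C (Approach) holds the only power statement in the Protocol: "A sample size of 44 achieves 81% power to detect 0.1 mean changes in circadian rhythm profiles measured by melatonin and circadian gene expression". The same sentence extends the claim to immune gene expression and carcinogenesis markers, and gives the remaining inputs as "an estimated standard deviation of differences of 0.3 under a significance level (alpha) of 0.05 using a two-sided paired t-test".

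The next sentence adds that "Power will be increased by using multivariable regression including other covariates that may affect the outcomes". The planned analysis is then described as "Repeated Measure ANOVA with two factors (alcohol, eating pattern) and their interaction", with a GEE model to handle further predictors.

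Under Aim 2 (anticipated results and pitfalls), the number of subjects is tied to this calculation and then raised for dropout: "We plan to recruit 55 subjects, assuming 20% drop out".

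**The concern.** A paired t-test calculation has five quantities: number of pairs, mean difference, SD of the differences, alpha with its sidedness, and power. The Protocol prints all five, so any four fix the other. A standardised effect of 0.1/0.3 = 0.333 is modest, and 44 pairs looked too few for it to give 81% power.

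The 44 and the 55 both depend on this sentence. If 0.1 and 0.3 are exact, a single paired comparison would miss a true change of 0.1 in 42% of such trials, where the Protocol implies 19%. If instead the intended change was larger and was rounded down for print, the Protocol understates the smallest effect it can reliably detect. Either way a reader cannot rely on the sentence as it stands.

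**Working it through.** **Inputs** (all from the statistics paragraph of Section C): n = 44; mean within-subject change δ = 0.1; SD of differences σ = 0.3; two-sided alpha = 0.05; paired t-test. In the crossover each subject receives all four conditions, so 44 subjects give 44 pairs for any paired contrast.

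**Attempt to reproduce the 81%.** Power comes from the noncentral t distribution with n − 1 degrees of freedom and noncentrality λ = (δ/σ)·√n.

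- λ = (0.1/0.3) × √44 = 0.3333 × 6.633 = 2.211; df = 43; critical value 2.017.
- Power = P(|T| > 2.017) = **58.0%**.
- Normal approximation: Φ(2.211 − 1.960) = 59.9%. Simulation with 100,000 runs: 58.3%.

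The stated figure is 23 points higher.

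**What would give 81%.**

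| Held fixed | Solved for | Result |
|---|---|---|
| δ = 0.1, σ = 0.3 | n | 75 (81.3%); 74 gives 80.8%; 73 gives 80.2% |
| n = 44, σ = 0.3 | δ | 0.4377 × 0.3 = 0.131 (0.130 for 80%) |
| n = 44, δ = 0.1 | σ | 0.1/0.4377 = 0.228 |

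Here 0.4377 is the standardised effect that gives 81% power at n = 44.

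**Other readings of the sentence.**

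- One-sided test at n = 44: 70.2%. The text says two-sided.
- All 55 recruits complete: 68.0%. The text says 44.
- 0.3 taken as the SD within each condition: 80% needs a within-subject correlation of about 0.7. The text says SD of differences and gives no correlation.
- Covariate gain already included: covariates would have to remove 1 − (0.2285/0.3)² = 42% of the variance of the differences. The text presents this gain as additional to the 81%.

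**Rounding.** A change of 0.131 prints as 0.1 and, with SD 0.3, gives 80.8%. An SD of 0.228 would not print as 0.3. Rounding of the SD alone cannot close the gap: δ = 0.1 with σ = 0.25, the smallest SD that rounds to 0.3, gives 74%. Joint rounding can: 0.11 with 0.25 gives 81.4%, and 0.14 with 0.32 gives 81.0%. If rounding is the whole explanation, the change must therefore exceed 0.1, by at least 0.4377 × 0.25 − 0.1 = 0.009.

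**Terms of the planned ANOVA** (illustration only). The Protocol gives neither an effect size for these terms nor a correlation. Assume an effect of 0.1, an SD of 0.3 for each of the two paired differences, and a correlation r between them. The interaction contrast then has SD 0.3·√(2(1 − r)), and the main effect averaged over the other factor has SD 0.3·√((1 + r)/2). With n = 44:

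| r | Alcohol-by-eating term | Averaged main effect |
|---|---|---|
| −0.2 | 29% | 93% |
| 0 | 33% | 86% |
| 0.25 | 42% | 78% |
| 0.5 | 58% | 70% |
| 0.7 | 80% | 65% |

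These equal 81% only at r of about 0.71 (interaction) or 0.16 (main effect). Neither value appears in the Protocol, and the test it names is a paired t-test.

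**Dropout step.** 44/0.8 = 55, so the inflation is correct; it simply inherits the 44.

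**The case against.** The strongest reply is rounding. Both 0.1 and 0.3 are printed to one significant figure. Values that round to them (0.05 to 0.15, and 0.25 to 0.35) span power from about 15% to 97% at n = 44, so 81% lies within that range. On this view the original calculation may be sound and only the printing careless. With a pair such as 0.11 and 0.25, the detectable change is understated by only 0.01. This stands as a possible cause, and the documents cannot exclude it. It does not rescue the sentence, because a power statement whose inputs are rounded until they no longer support it still has to be corrected.

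A second reply is that powering on a simple paired contrast and analysing by repeated-measures ANOVA is common, and that the choice of primary model term may sit in an analysis plan not shown here. That is fair. The ANOVA figures above depend on assumed correlations and an assumed interaction effect, and the finding does not rest on them. They show only why the text should say which comparison the power figure covers.

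A third reply is that this is a mechanistic study, and that Aim 2 also defends its size by crossover efficiency and by precedent from small circadian studies. Even so, Aim 2 names the calculation as the source of the 44, so the calculation should be right.

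**Conclusion.** The sentence is wrong as written. With the printed inputs taken at face value, power is 58%, against 81% stated, and the chance of missing a true change of 0.1 is 42% rather than 19%. The trial of 44 completers has 80% power for a change of 0.13 when the SD of differences is 0.3. These results assume only the test, alpha, SD and sample size that the Protocol itself names. Which printed figure is at fault (the power, the change or the SD) cannot be settled from the document. Since the recruitment target depends on it, the correction should be made.

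**What to change.** Retrieve the original calculation and make the sentence agree with it.

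- If 0.1 and 0.3 are exact, state that 44 subjects give 58% power for a mean change of 0.1 with an SD of differences of 0.3, or 80% power for a change of 0.13.
- If the calculation used other values (a change of about 0.13, an SD of about 0.228, or a pair in which both were rounded), print the change and the SD to enough decimals to reproduce the 81%, give their source, and keep the 81%.

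In either case, add that the figure applies to a single paired comparison and not to the alcohol-by-eating term. If power for an ANOVA term is also wanted, state the assumed effect and the assumed correlation between the paired differences.

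The cost is Protocol wording only, with no added enrolment. The drawback for the sponsor is a less favourable stated power or a larger stated detectable change.
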